2.1.3.3 Additional efficacy endpoints

Additional efficacy endpoints include endpoints from GSGC composite functional assessment, GMFM-88, hand-held dynamometry of upper extremity muscle groups (upper extremity muscle strength), 5-Level EuroQoL survey, and pediatric quality of life inventory.

Gait, Stair, Gower's Maneuver, and Chair composite functional assessment

Functional performance will be measured using the GSGC score. The GSGC total score can be obtained by adding the item scores of the four functional tests; item scores range from 1 to 7 for three items and 1-6 for one item (Arising from a chair). Briefly, total scores can vary from a minimum of 4 representing normal performance to a maximum of 27 representing the poorest functional score. The GSGC performance test has been validated for use with glycogen storage disease (GSD) type II patients and patients with Duchenne muscular dystrophy (19). Each of the functional items is also evaluated according to the time required to complete the task.

- Time to walk 10 meters (Gait),
- Time to climb 4 stairs (Stair),
- Time to stand from sitting on the floor (Gower's Maneuver),
- Time to stand from sitting position in a chair (Chair).

If a qualitative item is missing, total score will be missing. If timed item is missing, then this may be due to the item not being able to be completed (quality score of 6 or 7).

Gross Motor Function Measure-88 (GMFM-88)

The GMFM-88 (20) will be administered for all patients at the time points specified in the protocol to evaluate changes in motor function. Of the five dimensions to the GMFM-88, 2 dimensions (D and E) will be evaluated in this study:

- Standing (13 items),
- Walking, Running & Jumping (24 items).

Items were selected to represent motor functions typically performed by children without motor impairments by 5 years of age. Each item is scored on a 4-point Likert scale (ie, 0 = cannot do; 1 = initiates [$<10\%$ of the task]; 2 = partially completes [10% to $<100\%$ of the task]; 3 = task completion). The score for each dimension is expressed as a percentage of the maximum score for that dimension. Total score is obtained by adding the percentage scores for each dimension and dividing the sum by the total number of dimensions. Therefore, each dimension contributes equally to the total score. If an item is missing, the dimension score will be missing.

This assessment will include the expanded and revised Gross Motor Function Classification System for the GMFM-88 (gross motor function classification system-expanded and revised [GMFCS-E&R]) adapted for adults (21). The GMFCS emphasizes concepts in the World Health Organization's International Classification of Functioning, Disability and Health. Emphasis is on performance in home, work and community settings without judgments about quality of movement or prognosis for improvement. The GMFCS is a 5 level classification system consisting of Levels I to V based on self-initiated movement, with emphasis on sitting, transfers, and mobility. The distinctions between levels are based on functional limitations, the need for

assistive mobility devices, and to a much lesser extent, quality of movement, and are designed to be meaningful in daily life (21).

The general headings for the 5 levels (analyzed as 1, 2, 3, 4, 5) are:

- Level I Walks without limitations,
- Level II Walks with limitations,
- Level III Walks using a hand-held mobility device,
- Level IV Self-mobility with limitations; may use powered mobility,
- Level V Transported in a manual wheelchair.

Hand-held dynamometry (upper extremity muscle strength)

Upper extremity strength in the following muscle groups will be included:

- Shoulder Flexion,
- Shoulder Extension,
- Shoulder Abduction,
- Shoulder Adduction,
- Elbow Flexion,
- Elbow Extension,
- Grip Strength.

The limb tests will be completed bilaterally to account for differences in the generated force for the dominant and nondominant limb. Every muscle group will be measured two times and the highest value will be reported in the e-CRF. Patients may use noninvasive ventilation during the dynamometry assessment.

The summary score of the upper extremity strength will be the sum of the 14 measurements from the 7 muscle groups (left and right measurements from each muscle group). If any of the 14 measurements from the 7 muscle groups in extremity strength is missing, the summary score of the upper extremity strength is missing.

The percent predicted muscle strength will be calculated separately for muscle groups for which percent predicted equations are available; the percent predicted value of the total score for the upper extremity strength will be the average of the 12 percent predicted values from the 6 muscle groups. If any of the 12 measurements from the 6 muscle groups in percent predicted total score is missing, the percent predicted total score is not available.

No healthy predicted values are available for shoulder adduction for adults thus the following 6 muscle groups (both left and right side) are used in calculating the summary score.

- Shoulder Flexion,
- Shoulder Extension,
- Shoulder Abduction,
- Elbow Flexion,

- Elbow Extension,
- Grip Strength.

The reference equations to determine healthy predicted results for each muscle group are provided in [Table 10](#), [Table 11](#), and [Table 12](#). For the patients with age >16 at baseline, the predicted muscle strength will be calculated using the adult reference equations in [Table 7](#). For the patients with baseline age between 3 and 16 years old, the predicted muscle strength will be calculated using the pediatric reference questions in [Table 11](#) and [Table 12](#). For pediatric patients, the same reference equations will be used to calculate the predicted results from both left and right sides within each muscle group. For patients with baseline age between 3 and 16 years old, the predicted muscle strength normal reference is not available for shoulder flexion, shoulder extension, and shoulder adduction from existing publications; therefore, the summary score of the upper extremity muscle strength and supper extremity strength percent predicted will not be calculated.

Table 10 - ADULT HHD Reference Equations to Determine Healthy Predicted Result (N) (12) (13)

Muscle / Action (Reference)	Age=years; Gender: Male=1, Female=0; weight=kg, height=meters
Shoulder Flexion, Right, Left (1)	R: $9.8067 [-(age \times .14) + (gender \times 11.22) + ((weight/height^2) \times .22) + 16.85]$ L: $9.8067 [-(age \times .12) + (gender \times 10.68) + ((weight/height^2) \times .24) + 14.68]$
Shoulder Extension, Right, Left (1)	R: $9.8067 [-(age \times .17) + (gender \times 16.26) + ((weight/height^2) \times .17) + 23.35]$ L: $9.8067 [-(age \times .18) + (gender \times 14.64) + ((weight/height^2) \times .29) + 19.59]$
Elbow Flexion, Right, Left (1)	R: $9.8067 [-(age \times .13) + (gender \times 11.24) + ((weight/height^2) \times .07) + 22.78]$ L: $9.8067 [-(age \times .11) + (gender \times 10.63) + ((weight/height^2) \times .05) + 19.66]$
Elbow Extension, Right, Left (1)	R: $9.8067 [-(age \times .08) + (gender \times 8.33) + ((weight/height^2) \times .16) + 12.37]$ L: $9.8067 [-(age \times .07) + (gender \times 8.18) + ((weight/height^2) \times .17) + 11.32]$
Grip Strength, Right, Left (1)	R: $[-(age \times .18) + (gender \times 16.90) + ((weight/height^2) \times .23) + 31.33] / 2.20$ L: $[-(age \times .16) + (gender \times 16.68) + ((weight/height^2) \times .29) + 26.60] / 2.20$
Shoulder Abduction, Right, Left (2)	$178.90 - 77.1(gender) - 1.128(age) + .134(9.8067 \times weight)$

Table 11 - Pediatric muscle strength reference values in Newton (N) (14)

Muscle Group	Gender	Age												
		4	5	6	7	8	9	10	11	12	13	14	15	16
Shoulder Abductors	Boy	62	55	97	92	98	110	136	110	118	159	205	219	253
	Girl	68	47	75	91	94	91	81	129	123	154	178	173	173
Elbow Extensors	Boy			73	85	90	89	120	103	104	128	158	175	182
	Girl			73	85	82	91	84	108	117	118	129	141	107
Elbow Flexors	Boy	78	70	103	121	124	134	173	153	160	195	253	287	276
	Girl	69	66	105	103	115	125	134	172	168	201	193	198	215

Table 12 - Pediatric grip strength reference values (Mathiowetz, et al, 1986) (22)

Average Performance of Normal Subjects on Grip Strength (lb)

Age	Hand	Males			Females		
		Mean	SD	Range	Mean	SD	Range
6-7	R	32.5	4.8	21-42	28.6	4.4	20-39
	L	30.7	5.4	18-38	27.1	4.4	16-36
8-9	R	41.9	7.4	27-61	35.3	8.3	18-55
	L	39.0	9.3	19-63	33.0	6.9	16-49
10-11	R	53.9	9.7	35-79	49.7	8.1	37-82
	L	48.4	10.8	26-73	45.2	6.8	32-59
12-13	R	58.7	15.5	33-98	56.8	10.6	39-79
	L	55.4	16.9	22-107	50.9	11.9	25-76
14-15	R	77.3	15.4	49-108	58.1	12.3	30-93
	L	64.4	14.9	41-94	49.3	11.9	26-73
16-17	R	94.0	19.4	64-149	67.3	16.5	23-126
	L	78.5	19.1	41-123	56.9	14.0	23-87
18-19	R	108.0	24.6	64-172	71.6	12.3	46-90
	L	93.0	27.8	53-149	61.7	12.5	41-86

Note: The mean scores for individuals, aged 14 to 19 years, may be slightly low (0-10 lb lower than they should be) due to instrument error detected after the study.

5-Level EuroQol in 5 dimensions

The EQ-5D-5L is a standardized instrument for use as a measure of health outcome (23). Applicable to a wide range of health conditions and treatments, it provides a simple descriptive profile and a single index value for health status. The EQ-5D-5L descriptive system comprises 5 dimensions of health (mobility, self-care, usual activities, pain/discomfort, anxiety/depression). Each dimension has 5 levels of health/ability (type of response could be no problem, slight problem, moderate problem, severe problem; or unable to perform activity or no, slight, moderate, severe, or extreme). The EQ VAS records the respondent's self-rated health status on a vertical graduated (0-100) visual analogue scale. A score of 100 represents the best imaginable health state and 0 refers to the worst imaginable health state.

Patients who are ≥18 years of age at screening/baseline will complete this assessment.

Pediatric quality of life inventory

The PedsQL Generic Core Scale (24, 25) is an instrument that was designed to measure HRQoL in healthy children, as well as those with acute and chronic health conditions, covering an age spectrum in the range of 2–18 years. During the treatment period, the patients will continue on the age-specific assessment they first completed at screening/baseline, even if they exceed the age range for that specific tool over the trial duration. The PedsQL comprises parallel child self-report (age 5–7 years [young child], 8–12 years [child] and 13–18 years [adolescent]) and parent proxy-report (age 2–4 years [toddler], 5–7 years [young child], 8–12 years [child] and 13 to 18 years [adolescent]) formats. The PedsQL generic core scales were specifically designed to measure the core dimensions of health as delineated by the World Health Organization, as well as role (school/day care) functioning. It contains 23 items that are grouped to create four sub-scales of PF: 8 items), Emotional Functioning (EF: 5 items), (SF: 5 items), and School Functioning (Sch F: 5 items).

A 5-point response scale is applied across each item (0 = never a problem; 1 = almost never a problem; 2 = sometimes a problem; 3 = often a problem; 4 = almost always a problem). Items are reverse scored and linearly transformed to a 0–100 scale (0 = 100, 1 = 75, 2 = 50, 3 = 25, 4 = 0) with higher scores indicating better HRQoL. For scale and total scores, the mean is computed as the sum across all items divided by the number of items answered, thereby accounting for missing data if present. The Physical Health Summary Score (8 items) is the same as the PF Subscale. To create the Psychosocial Health Summary Score (15 items), the mean is computed as the sum of the items divided by the number of items answered in the Emotional, Social, and Sch F Subscales. If more than 50% of the items in the scale are missing, the Scale Score should not be computed. Imputing the mean of the completed items in a scale when 50% or more are completed is generally the most unbiased and precise method. To do this, count the number of missing values in the scale (call it nmiss). Next, sum the item scores and divide by the number of items in the scale minus nmiss.

The questionnaire was developed through focus groups and cognitive interviews. The results demonstrate the reliability and validity of the PedsQL 4.0 Generic Core Scales. Internal consistency reliabilities generally exceeded the standard of 0.70 for group comparisons. Across the ages, the Total Scale Score for self-report and proxy-report approached an alpha of 0.90, recommended for individual patient analysis, making the Total Scale Score suitable as a summary score for the primary analysis of HRQOL outcomes in clinical trials and other group comparisons. The Physical Health and Psychosocial Health Summary Scores are recommended for secondary analyses. The Sch F Subscales for proxy-report for ages 2 to 4 and self-report for ages 5 to 7 were the only two Subscales that did not approach or exceed 0.70. The Emotional, Social, and Sch F Subscales may be utilized to examine specific domains of functioning, with the caveat that until further testing is conducted, these Subscales should be used for descriptive or exploratory analyses.

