9.3 OTHER ENDPOINTS

9.3.1 Tertiary efficacy endpoints

9.3.1.1 *Gait, Stair, Gower's Maneuver, and Chair composite functional assessment*

Functional performance will be measured using the GSGC score at the time points specified in [Section 1.2](#). During the treatment period, the assessment will be completed before IMP infusion. The GSGC total score can be obtained by adding the item scores of the 4 functional tests; item scores range from 1 to 7 for 3 items and 1 to 6 for 1 item (Arising from a chair). Total scores can vary from a minimum of 4 representing normal performance to a maximum of 27 representing the poorest functional score. The GSGC performance test has been validated for use with glycogen storage disease (GSD) type II patients and patients with Duchenne muscular dystrophy (10). Each of the functional items is also evaluated according to the time required to complete the task.

- Time to walk 10 meters (Gait);
- Time to climb 4 stairs (Stair);
- Time to stand from sitting on the floor (Gower's Maneuver);
- Time to stand from sitting position in a chair (Chair).

See the study specific manual for further details.

9.3.1.2 *Gross Motor Function Measure*

The GMFM-88 (11) will be administered at the time points specified in [Section 1.2](#) to evaluate changes in motor function. During the treatment period, the assessment will be completed before IMP infusion. The GMFM-88 was developed specifically to detect quantitative changes in gross motor function. There is no age cut-off for the GMFM-88.

Of the 5 dimensions to the GMFM-88, 2 will be evaluated in this study:

- Standing (13 items);
- Walking, Running & Jumping (24 items).

Items were selected to represent motor functions typically performed by children without motor impairments by 5 years of age. Each item is scored on a 4-point Likert scale (ie, 0 = cannot do; 1 = initiates [$<10\%$ of the task]; 2 = partially completes [10% to $<100\%$ of the task]; 3 = task completion). The score for each dimension is expressed as a percentage of the maximum score for that dimension. Total score is obtained by adding the percentage scores for each dimension and

dividing the sum by the total number of dimensions. Therefore, each dimension contributes equally to the total score.

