2.5.1 Analysis of primary efficacy endpoint in PAP

The primary efficacy endpoint of change from baseline in FVC (% predicted) in upright position to Week 49 will be analyzed in the mITT population using MMRM with change from baseline as the outcome variable. The MMRM model will include the baseline FVC (% predicted) and age (both as continuous variables), gender (male or female), treatment group, visit, and treatment-by-visit interaction as fixed effects.

The analysis will include all post baseline scheduled assessments up to Week 49, regardless of treatment discontinuation status; missing data will not be imputed and will be assumed to be Missing at Random (MAR). Descriptive assessment of MAR assumption and sensitivity analyses to assess the impact of missing data are described in [Section 2.5.3](#).

An unstructured covariance matrix shared across treatment groups will be used to model the within-patient errors. The model will be fitted using restricted maximum likelihood. If the model does not converge with an unstructured covariate matrix, the following covariate matrix structures will be used in the order of heterogeneous Toeplitz (heterogeneous variance, an extension of homogeneous Toeplitz), homogeneous Toeplitz (equal variance and a separate correlation for each level of separation between the time points), heterogeneous AR(1) (heterogeneous variance, an extension of AR(1)), AR(1) (first-order autoregressive, equal variances and exponentially decreasing correlations). The first covariance structure yielding convergence will be used as the primary analysis.

The Kenward-Roger approximation will be used to estimate the denominator degrees of freedom. The difference between treatment groups will be estimated based on least-square means at the Week 49 visit within the MMRM model. A two-sided 95% confidence interval using the estimate and variance of the least-square mean difference will be provided.

Due to the small sample size within each country or region, the primary MMRM will not include region/country as a covariate. Also, since previous alglucosidase alfa studies did not suggest a baseline-by-visit interaction within either study treatment arm, the primary MMRM will not include the baseline-by-visit interaction in the model to improve statistical efficiency.

The primary analyses will be performed after all randomized patients have been followed for at least 12 months (49 weeks) after randomization (or discontinued the study follow-up early).

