2.5.5 Additional efficacy analyses including PRO endpoints

All other exploratory efficacy endpoints will be summarized descriptively and analyzed using a similar method for the primary efficacy endpoint described in [Section 2.5.1](#). For PDSS/PDIS, following the scoring method and algorithm, results will be summarized by descriptive statistics, MMRM, and responder analysis. The analyses will be based on mITT population.

Analyses of efficacy data in extension treatment (ETP)

Unless otherwise specified, ETP efficacy analyses will use the mITT population, where patients will be considered to be in the treatment group to which they were randomized.

All efficacy endpoints will be summarized descriptively at each study visit, as well as the last observation available during the study. For study visits in ETP (beyond week 49), both changes from baseline and changes from ETP baseline (week 49) will be presented.

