2.10.3 Missing data handling in data presentation

In general, missing baselines will not be imputed. The following approaches are default methods for missing data handling in summary tables.

- Categorical data at baseline will be summarized for each treatment group using counts (n) and percentages (%). Denominator will be the analysis population specified for the summary, unless otherwise specified. Missing data may be presented as a separate category.
- Continuous data: The analyses and summaries for variables with continuous scales will be based on observed data only.

Handling of computation of treatment duration if investigational medicinal product end of treatment date is missing

For the calculation of the treatment duration, the date of the last dose of IMP is equal to the date of last administration reported on drug exposure case report form page. If all the infusion dates are missing, then the duration is missing.

The last dose intake should be clearly identified in the case report form and should not be approximated by the last returned package date.

Handling of missing/partial dates for adverse events or concomitant medications

Missing or partial adverse event onset dates and times will be imputed so that if the partial adverse event onset date/time information does not indicate that the adverse event started prior to treatment or after the treatment-emergent adverse event period, the adverse event will be classified as treatment-emergent. No imputation of adverse event end dates/times will be

performed. These data imputations are for categorization purpose only and will not be used in listings. No imputation is planned for date/time of adverse event resolution.

No imputation for medication start/end dates or times will be performed. If a medication date or time is missing or partially missing and it cannot be determined whether it was taken prior or concomitantly, it will be considered a prior, concomitant, and post-treatment medication.

Handling of missing or partial birth date for calculation of age

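### A missing GSGC task time can mean the patient could not do the task, but the plan analyses only observed times under MAR, so loss of ability is hidden or understated in the timed items

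*SAP*

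**What the plan says.** Protocol 9.3.1.1 and SAP 2.1.3.3 score four tasks (10 m walk, four stairs, rising from the floor, rising from a chair) and add that "Each of the functional items is also evaluated according to the time required to complete the task". In the SAP the quality "item scores range from 1 to 7 for three items and 1-6 for one item (Arising from a chair"), with high scores poor.

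SAP 2.1.3.3 has one missing-data rule for the quality scores: "If a qualitative item is missing, total score will be missing". For the times it only comments that "this may be due to the item not being able to be completed (quality score of 6 or 7"). It does not say how such a time enters the analysis, or which score means unable on which item.

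Three general rules then apply:

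- SAP 2.5.5: "All other exploratory efficacy endpoints will be summarized descriptively and analyzed using a similar method for the primary efficacy endpoint". In that method (2.5.1), "missing data will not be imputed and will be assumed to be Missing at Random (MAR").
- SAP 2.10.3: "The analyses and summaries for variables with continuous scales will be based on observed data only".
- SAP 2.10.2: a patient with no baseline value is left out of the MMRM.

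The tipping-point analysis in SAP 2.5.3.1 covers FVC only.

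**The concern.** A patient who climbed the stairs slowly at baseline and can no longer climb them at Week 49 has had the worst outcome on that item, yet has no Week 49 time. The mean time is then taken over those still able, which is itself an outcome after randomisation. The arm that preserves more function keeps its slow patients in the average; the other arm sheds them. MAR is doubtful because the time is absent on account of how poor performance was at that visit. Earlier slow times help the model only in part.

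The reverse also happens. Protocol 7.2.1 requires patients to walk 40 m at entry but sets nothing for stairs, floor or chair. Someone unable at baseline who regains a task has no baseline time, so the gain is not counted.

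At stake is how readers interpret timed function by arm, not the trial's formal conclusions.

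**Working it through.** The plan states no figure for GSGC times, so there is none to reproduce. Every input below is an assumption, chosen to show the direction and rough size of the bias.

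**Check 1: one follow-up visit, 400,000 patients per arm.**

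- Baseline time: B = 8·exp(0.6·Z) s, so the mean is 8·exp(0.6²/2) = 9.58 s.
- Week 49 time: F = 1.05·B·exp(w·E), identical in both arms, where w is the within-patient log-SD and Z and E are standard normal.
- The slowest 5% or 10% of one arm become unable and their times go missing. Nobody in the other arm does.
- With w = 0 the true mean change is 0.05 × 9.58 = 0.48 s in each arm. With w = 0.25 it is 9.58 × (1.05·exp(0.25²/2) − 1) = 0.80 s.

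*Loss decided by baseline time, w = 0.* The observed mean change is 0.48 s in the arm that keeps function. In the losing arm it is 0.43 s (5% unable) or 0.40 s (10% unable). The losing arm looks faster by 0.05 or 0.08 s in a raw summary. After regression on arm and baseline time, which is how I read a method similar to the primary, the gap is about 0 s. It stays about 0 s for w up to 0.3.

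*Loss decided by the unseen Week 49 time.* Baseline adjustment no longer removes the bias. The losing arm appears faster, after adjustment, by:

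| Within-patient log-SD (w) | 5% unable | 10% unable |
|---|---|---|
| 0.15 | 0.11 s | 0.16 s |
| 0.20 | 0.19 s | 0.28 s |
| 0.25 | 0.28 s | 0.42 s |
| 0.30 | 0.40 s | 0.60 s |

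If the item is analysed as speed, with 0 for unable, the arm that keeps function comes out ahead in every one of these runs.

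**Check 2: baseline plus four visits, 40,000 per arm, unstructured normal likelihood under MAR.** This is the large-sample counterpart of the planned MMRM. Assumed mean 5 s, SD 2.5 s, correlation between visits 0.5 or 0.8. In the two decline scenarios, a time above 12 s is recorded as unable. Differences are losing arm minus stable arm.

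- *Rapid decline to inability in 5%, 10% or 20% of one arm:* the true difference is about 0.6, 1.2 and 2.4 s. Observed times show about 0 s. The MMRM shows 0.12, 0.19–0.26 and 0.44–0.57 s. For example 0.19/1.19 = 16% and 0.57/2.41 = 24%, so roughly 75–85% of the harm is lost.
- *Slower decline:* true 0.29–1.23 s, MMRM 0.18–1.01 s. The deficit is shrunk but visible.
- *Arms alike except that the slowest 5–20% of one arm become unable at Week 49:* that arm appears faster by 0.08–0.63 s in the MMRM.

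These fits estimate the covariance within each arm. Sharing it across arms, as the SAP plans, gives much the same picture (0.08–0.58 s in the last scenario).

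**Check 3: a whole arm shifted slower by 0.25 to 1.0 SD, with a common cut-off for ability.** The observed difference shrinks to 0.15–0.77 SD and does not change sign.

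**The case against.** The best defence is that inability is already counted where it matters. The endpoint named in both documents is the GSGC score; a patient who loses a task moves to 6 or 7 on that item and worsens on the total, and one who regains it improves. The times are an extra descriptor. GSGC is tertiary (Protocol 9.3.1) and absent from the hierarchy (Protocol 11.4.2.3, SAP 2.5.2). All of this stands and limits the importance of the point, but it does not correct the timed results.

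The link to the MMRM is also loose: SAP 2.5.5 speaks of exploratory endpoints, while the protocol calls GSGC tertiary. That is fair, but the observed-only rule in 2.10.3 would still govern the summaries by visit. Administration details sit in a study manual that is not available here; it might separate unable from not attempted, but the SAP does not use any such code for the times.

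Baseline adjustment is a real protection. Where loss of ability follows baseline slowness it removes the bias. It does not do so where loss follows deterioration during the trial.

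A reader might infer that the arm losing function will look better than its comparator. The documents do not support that as a general result: in several scenarios the deficit is only shrunk or hidden, and reversal needs arms that are otherwise alike. Nor does every missing time mean inability; the SAP says only that it may.

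**Conclusion.** The point holds in a limited form. The SAP identifies a reason for missing times that is itself a poor outcome, then leaves those times to rules that ignore it. In all the scenarios where bias remains, it makes the arm losing function look better than it is. Its size cannot be fixed from the documents, which give no GSGC time distribution, inability rate or test time limit. Under the inputs of Check 1 (median 8 s, log-SD 0.6, within-patient log-SD 0.15–0.3, 5–10% unable in one arm) it runs from about 0 s, when loss depends on baseline time, to about 0.1–0.6 s, when it depends on the unseen Week 49 time.

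A reader might also infer a threat to the trial's main conclusions. There is none: FVC, the 6MWT and the rest of the hierarchy are untouched, and the GSGC total score retains inability.

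**What to change.** In SAP 2.1.3.3 and 2.5.5:

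- State, for each item, which quality score means the task could not be completed. The chair item ends at 6 and the other three at 7, so the present comment does not settle it.
- Report the number unable per item, arm and visit beside each timed result. This is the minimum.
- Analyse each timed item with inability as the worst outcome: speed (10 m/time, 4 stairs/time, 1/time to rise) set to 0 when that item's score at that visit records inability. Assigning the worst rank would serve equally well.
- Use the same coding at baseline, so that a patient who regains a task counts as improved.
- Leave the value missing only when the item was not attempted for another reason.

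The cost is SAP wording and a derivation from scores already collected. The drawback is that speeds or ranks are less familiar than seconds; observed times can still be tabulated if labelled as times among those able.

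### SAP 2.1.3.3 defines the upper-extremity HHD summary score in two conflicting ways, cites a lower-limb table for adults, and withholds the raw composite at ages 3 to 16 for a reason that applies only to percent predicted

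*SAP*

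**What the plan says.** All of the text at issue is in the upper-extremity HHD part of SAP 2.1.3.3.

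- **First definition.** "The summary score of the upper extremity strength will be the sum of the 14 measurements from the 7 muscle groups", with both sides counted. One absent reading out of the 14 is enough to make this score missing.
- **Percent predicted.** This is a separate quantity. The total for "upper extremity strength will be the average of the 12 percent predicted values from the 6 muscle groups".
- **Second definition.** "No healthy predicted values are available for shoulder adduction for adults thus the following 6 muscle groups (both left and right side) are used". The sentence closes by naming the summary score as the quantity these groups feed, and the list that follows omits shoulder adduction.
- **Adult reference.** Tables 10, 11 and 12 are introduced as the upper-limb references. The next sentence has the prediction for patients over 16 made "using the adult reference equations in [Table 7".
- **Ages 3 to 16.** Norms are missing for shoulder flexion, extension and adduction, and therefore "the summary score of the upper extremity muscle strength and supper extremity strength percent predicted will not be calculated".

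Protocol 9.3.1.3 lists the same 7 muscle groups, tested on both sides, with no age limit. Protocol 17.3.3 no longer requires HHD at Canadian sites.

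**The concern.** One name, the summary score, is attached to two different sums. Which one is analysed would depend on which sentence the programmer follows, and the choice also changes who has a score. The composite is used in analyses: SAP 2.5.1.3 includes the upper- and lower-limb composites in the analysis restricted to the same assessor and position, and SAP 2.5.5 applies a method like the primary one to the other exploratory efficacy endpoints. A score definition should not be left to be settled while outputs are being programmed.

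Two further instructions in the same paragraphs do not work as written. The adult percent-predicted score cannot be computed from the table cited. The raw composite at ages 3 to 16 is dropped for want of values that it does not use, although the protocol's introduction says that the study will evaluate response in treatment-naïve paediatric patients.

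**Working it through.** This is a comparison of definitions. No power or error-rate calculation applies.

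**1. Counts.** The inputs are the muscle-group lists in SAP 2.1.3.3, each group tested on two sides.

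- First definition: 7 × 2 = 14 readings, as the SAP states.
- Second definition: 6 × 2 = 12 readings.
- Relation: S14 = S12 + adduction (right) + adduction (left). The same holds for change from baseline, so an estimated treatment difference on S14 also contains the difference in the two adduction changes.
- Size: 2/14 = 14.3% of the readings. The share of total force cannot be derived, because the documents give no shoulder adduction values.

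**2. Missing data.** Under the first definition, one missing adduction reading makes the score missing. Under the second, adduction is not an ingredient, so its absence cannot. The SAP states a rule for 12 measurements only for the percent-predicted total, not for a 12-reading raw sum.

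**3. Does the rest of the SAP settle 14 or 12?** The lower-limb text in SAP 2.1.3.2 is the natural comparator.

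| | Groups tested | Groups in raw sum | Readings summed |
|---|---|---|---|
| Lower limb | 8 | 6 (plantar flexion and hip adduction dropped for lack of norms) | 12 |
| Upper limb, first definition | 7 | 7 | 14 |
| Upper limb, second definition | 7 | 6 (shoulder adduction dropped for lack of norms) | 12 |

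The second definition follows the lower-limb convention. The first is the more explicit, with its own count and missing-data rule. The text does not decide between them.

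**4. Adult reference table.** The six upper-limb groups are shoulder flexion, shoulder extension, shoulder abduction, elbow flexion, elbow extension and grip.

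- Table 7 rows are hip flexion, hip extension, hip abduction, knee flexion, knee extension and ankle dorsiflexion. Overlap: 0 of 6.
- Table 10 rows are the six upper-limb groups. Overlap: 6 of 6.

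This checks coverage only, not the correctness of each Table 10 equation.

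**5. Ages 3 to 16.** The raw score under either definition is a sum of observed readings with no reference value in it. Missing norms prevent a percent-predicted total; they do not prevent the sum. The lower-limb rules show the distinction. SAP 2.1.3.2 says that norms for most lower-limb groups start at age 6. SAP 2.5.1.3 then limits the percent-predicted analysis to age 6 or older and states no age limit for the raw composite.

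**The case against.** The best defence is that the paragraph with the second definition is about percent predicted. It opens with the average of 12 values, and the disputed sentence begins with the lack of predicted values. If summary score there is read as percent-predicted total, the raw score is 14 throughout and the conflict disappears. Table 7 is plainly a cross-reference slip, since the sentence before it names the right tables.

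Part of this stands. A wording slip is a plausible explanation, and the Table 7 error is self-evident. A reader might infer that adults would receive wrong predicted values from lower-limb equations. The documents do not support that, because Table 7 has no shoulder, elbow or grip row from which to compute one.

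The defence does not remove the conflict. The same section later names the summary score and percent predicted as two separate things, so the terms are not interchangeable there. The lower-limb section uses the same argument, that groups without norms are left out, and it does reduce the raw sum to 12 readings. A programmer following that precedent would drop adduction and would be reading the SAP reasonably.

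That precedent cuts the other way too. It is tempting to conclude that 14 is correct because a raw sum needs no norms. The SAP already restricts a raw sum to groups with norms for the lower limb, so its text does not select 14 over 12.

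**Conclusion.** The point holds as an internal inconsistency in SAP wording: two raw definitions that differ by 2 of 14 readings and in their missing-data rule, an adult percent-predicted instruction that cannot be carried out as written, and a raw composite withheld at ages 3 to 16 for a reason that does not apply to it.

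The consequence is small. Upper-extremity HHD is a tertiary endpoint, absent from the testing sequence in Protocol 11.4.2.3 and SAP 2.5.2, so no primary or confirmatory conclusion depends on it. SAP 1.1 expects few patients under 18. Children enrolled directly into the open-label phase are outside the randomized population, and their efficacy results are only listed (SAP 2.2 and 2.3).

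Two stronger readings should be resisted. A reader might infer that children's strength data are discarded. Only the composite and the percent-predicted score are withheld; the SAP does not discard individual muscle-group readings, and nothing shows that every child completed all of them. A reader might also infer that every adult's score is affected. The ambiguity reaches only patients with HHD data, and Canadian sites are no longer required to collect it.

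The conclusion rests on taking the SAP's terms as written. If the sponsor confirms that the second sentence meant percent predicted, the first part reduces to a wording correction.

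**What to change.** Make three edits to SAP 2.1.3.3 before unblinding:

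1. State one definition of the raw upper-extremity summary score: either 14 readings from 7 groups, or 12 readings from 6 groups to match the lower-limb convention. Use it in both places, with a missing-data rule that counts the same readings. Keep the percent-predicted total under its own name, as the average of 12 values.
2. For patients over 16 at baseline, replace the reference to Table 7 with Table 10.
3. At ages 3 to 16, withhold only the percent-predicted total. Calculate the raw summary for any child with complete readings.

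If the primary-period unblinding has already taken place, record which raw definition was programmed and report the other beside it.

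The cost is SAP wording and matching programming specifications. No new data, visits or patients are needed, and the testing hierarchy is unchanged.
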